After BBTI training, and enrolling in the study, PCMHI clinicians will undergo individual mock sessions with their site PI to ensure competency, as rated using the BBTI Competency Rating Scale (BBTI-CRS [see appendix]; adapted from the Cognitive Therapy Rating Scale). A score  $\geq 50\%$  (or  $\geq 2$  for each item) is passing and if  $<50\%$ , PCMHI clinicians can review materials and work with their site PI until they pass.

Table 2. PCMHI 5A functional assessment for insomnia.

| 5As    | Definition and Application to Insomnia                                                                                                                                                                                                                                                                                                                                                                                                                                                                                                                                           |
|--------|----------------------------------------------------------------------------------------------------------------------------------------------------------------------------------------------------------------------------------------------------------------------------------------------------------------------------------------------------------------------------------------------------------------------------------------------------------------------------------------------------------------------------------------------------------------------------------|
| Assess | 
 
• Introduce role of PCMHI clinician (1-2 minutes)
 
• Identify/clarify problem (10-60 seconds) – ensure insomnia is the key complaint
 
• Functional analysis of problem (12-15 minutes) – assess for insomnia diagnostic criteria, impact on function and quality of life, administer self-report measures (e.g., ISI, PHQ-9, etc.), brief history of prior or current treatment efforts (e.g., sedative-hypnotics)
 
• Summarize understanding of problem (1-2 minutes) – re-affirm functional analysis
 
 |

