| 
CFIR: Learning climate
                                                           | 
Example: Site PIs will meet regularly with their local PCMH clinicians (e.g., monthly by phone) to discuss implementation efforts, both successes and setbacks. They will also engage with local clinical stakeholders (i.e., Primary Care teams). Also, during scheduled and ad hoc calls, external facilitators at the coordinating site will provide guidance regarding barriers towards implementation and work with site PIs to reinforce successful strategies with their local PCMH clinicians.
                                                                                                                                                                                                                                      |
| 
6.
ERIC: Increase demand with marketing to patients
                          | 
Marketing to Veterans can increase awareness, referrals, and same-day access of BBTI in PCMH. Potential methods to be used: (1) letters mailed directly to Veterans prior to upcoming Primary Care appointments; and (2) signs, brochures, and other educational information in Primary Care clinics regarding BBTI services and encouraging Veterans to discuss sleep issues with their Primary Care team; (3) digital educational products (e.g., short video) that can be shown to Veterans by providers and/or posted on VA websites (e.g., Facebook, YouTube). The process of identifying Veterans prior to appointments, and the creation of marketing materials, will be managed by the coordinating site and executed locally by site PIs.
 |
| 
CFIR: Peer pressure
                                                              | 
Example: The coordinating site will identify Veterans with an insomnia diagnosis and/or prescription for a sedative-hypnotic medication who have a Primary Care appointment in the next month. This information will be forwarded to site PIs, who can then mail information to these Veterans about BBTI in Primary Care and encourage them to discuss sleep-related problems with their PCP.
                                                                                                                                                                                                                                                                                                                                              |

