### **5.4 Inclusion/Exclusion Criteria**

Site PIs and PCMH clinician are the focus of this study with retrospective data collection for Veterans who receive BBTI (or CBT-I) delivered by PCMH clinician at the participating sites. Each participating site PI will be invited to participate in this study. PCMH clinician at each participating site will be invited, by their site PI, to attend a training for BBTI. Those who attend and complete BBTI training will be invited to participate in this study. PCMH clinician who have been previously training in CBT-I will not be required to take the BBTI training as BBTI is adapted from CBT-I and there is significant overlap. Women and minorities will be included in this study.

There will be retrospective data collection from electronic health records and databases for Veterans who receive care in PCMH and engage in BBTI (or CBT-I) from a PCMH clinician.

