|                    |            |                                                                                                                  |
|--------------------|------------|------------------------------------------------------------------------------------------------------------------|
| Diagnoses          | ICD-10:    | F51.0, F51.01, F51.02, F51.03, F51.04, F51.05, F51.09, G47.00, G47.01, G47.09                                    |
|                    | ICD-9:     | 307.41, 307.42, 780.50, 780.51, 780.52                                                                           |
| Sedative-hypnotics | On label:  | diphenhydramine, doxepin, eszopiclone, prazosin, ramelteon, suvorexant, temazepam, triazolam, zaleplon, zolpidem |
|                    | Off label: | hydroxyzine, melatonin, trazodone, others specifically indicated for sleep                                       |

Effectiveness will be measured as the change on the ISI from the initial score obtained (e.g., PCMH initial evaluation, BBTI/CBT-I session 1) to the last BBTI/CBT-I session. The ISI is commonly used within the VA and is easily accessible within VA electronic health records through the Mental Health Assistant toolbox as well as Behavioral Health Lab software, which was developed for use in PCMH. ISI data may also be extracted from CPRS progress notes (e.g., BBTI progress notes). The ISI has well-established psychometrics with good reliability and validity. It is standard practice as part of insomnia-related treatment (i.e., BBTI and CBT-I) and PCMH treatment (e.g., depression, anxiety, pain) to use measurement-based care (e.g., ISI, PHQ-9) and include outcome measures in progress notes to inform care and track treatment progress. For Effectiveness to be calculated, ISI scores from each BBTI/CBT-I session (e.g., entered in a BBTI progress note or CBT-I templated note) by PCMH clinicians will be extracted through the automated CDW queries to calculate outcomes for each Veteran. Rates of treatment response and remission will also be calculated. Response is a reduction of ≥8 points on the ISI from pre- to post-treatment. Remission is achieving a post-treatment response and an ISI <8. Previous BBTI trials found treatment response rates of 42-77% and remission rates of 28-53%.

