Maintenance will measure the sustainability of Reach, Effectiveness, Adoption, and Implementation during the 6-month post-implementation phase as well as during the long-term sustainability period (>6-months). The outcomes from the sustainability periods will then be compared to the outcomes during the pre- and implementation phases. The same operational definitions as described above will be used for Reach, Effectiveness, and Implementation. For Adoption, comparisons will be based on the rate a clinician delivers BBTI over time within each study phase. For example, the number months a PCMHI clinician Adopts BBTI (i.e., delivers BBTI to a Veteran) relative to the number of months [n=6] in the post-implementation phase.

Specific Aim 2: To identify specific strategies that help promote the implementation of BBTI in PCMHI using qualitative interviews and utilization surveys.

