For treatment Effectiveness, using an intent-to-treat approach, we will fit a linear mixed model that tests for BBTI effectiveness (reduction of ISI score over the course of treatment) that includes a main effect of time (evaluation to last treatment session) and includes random effects for Veteran (multiple measurements per Veteran during treatment), clinician (nesting of Veterans within clinicians) and site (nesting of Veterans and clinicians within site). We will also attempt to control for clinician experience on treatment outcomes as well as mode of delivery of BBTI (e.g., in-person, phone, video) and other adaptations, such as integrating other

therapeutic techniques as indicated per the progress notes and extracted as part of the data query process (e.g., behavioral activation, motivational interviewing). Rates of response and remission from treatment will be calculated as will treatment effect sizes.

Specific Aim 2: To identify specific strategies that help promote the implementation of BBTI in PCMH using qualitative interviews and utilization surveys.

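### Effectiveness is to be compared between study phases without adjustment for initial ISI, so any phase difference in intake severity could shift response or remission with treatment unchanged

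*Combined protocol and SAP*

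**What the plan says.** Section 5.5 measures Effectiveness as ISI change from the initial score to the last BBTI or CBT-I session, and adds two rates. "Response is a reduction of ≥8 points on the ISI from pre- to post-treatment". "Remission is achieving a post-treatment response and an ISI <8". Section 5.4 collects data "for Veterans who receive care in PCMH and engage in BBTI (or CBT-I) from a PCMH clinician" and sets no minimum ISI. The intake in Table 2 (section 5.1) tells clinicians to "assess for insomnia diagnostic criteria" and to administer the ISI, but requires no score.

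Several places look at Effectiveness by phase. Aim 1 (section 3.1) hypothesises better treatment outcomes under BBTI+IS. Section 5.5 plans within-site comparisons of the RE-AIM variables from phase to phase. Under Maintenance, which covers Effectiveness, it says: "The outcomes from the sustainability periods will then be compared to the outcomes during the pre- and implementation phases".

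The Effectiveness model in section 5.6 "includes a main effect of time (evaluation to last treatment session) and includes random effects for Veteran", clinician and site. The covariates it hopes to control for are clinician experience, mode of delivery and therapeutic adaptations. It names neither initial ISI nor study phase. Response and remission are to be calculated, with no model. ISI scores appear among the descriptive Veteran variables.

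**The concern.** The bundle is meant to change who reaches treatment. Table 3 adds education of Primary Care teams and patient marketing; of the latter it says: "Marketing to Veterans can increase awareness, referrals, and same-day access of BBTI in PCMH". If Veterans who start during implementation are milder or more severe than those who start before it, the chance of losing 8 points, or of losing 8 points and ending below 8, changes even when treatment works equally well. A crude comparison would then credit or blame the bundle for a change in intake. The stake is the Effectiveness part of the Aim 1 hypothesis and its Maintenance comparison. The primary outcome, Reach, is not touched.

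**Working it through.** The plan gives no target, sample size or power for response or remission, so it has no figure of its own to reproduce.

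**What follows from the definitions alone.** From an initial ISI of 15 or more, ending at 7 or less already means a drop of at least 8, so the response clause in remission bites only below 15 (14 to 7 is a 7-point drop, and so neither response nor remission). Both outcomes therefore depend on the starting score.

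**Inputs from the documents.** The VA CBT-I study cited in section 2.1 reports mean ISI 20.7 to 10.9, d = 2.3, and 60% response among completers. Mean drop = 20.7 − 10.9 = 9.8 points; proportional drop = 9.8 / 20.7 = 47.3%.

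**Assumptions.** Baseline SD 4.3 (9.8 / 2.3 = 4.26, if d was scaled by that SD). Mean initial ISI is 20.7 in one phase and 18 or 16 in another; these shifts are illustrative. Equal treatment is taken in two ways: the same proportional drop (mean 47.3%, SD 0.2 or 0.3) or the same point drop (mean 9.8, SD 4.3 or 7).

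**Check against the cited 60%.** With change SD 7, P(drop ≥ 8) = Φ((9.8 − 8) / 7) = Φ(0.257) = 60.1%. With SD 4.26, it is 66% without and 71% with a half-point rounding correction. The documents do not give the change SD.

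**Simulation.** 2,000,000 Veterans per setting, ISI rounded to integers and limited to 0–28. Results for mean initial ISI 20.7 / 18 / 16:

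| Equal treatment means | SD of drop | Response, % | Remission, % |
|---|---|---|---|
| Same proportional drop | 0.2 | 66.9 / 56.4 / 46.8 | 22.1 / 25.9 / 26.4 |
| Same proportional drop | 0.3 | 61.8 / 54.1 / 46.9 | 29.9 / 32.7 / 32.8 |
| Same point drop | 4.3 points | 70.3 / 69.8 / 68.7 | 27.6 / 41.5 / 50.2 |
| Same point drop | 7 points | 62.8 / 62.4 / 61.3 | 33.1 / 43.3 / 49.1 |

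Moving from 20.7 to 18:
- Proportional drop: response falls 66.9 − 56.4 = 10.5 or 61.8 − 54.1 = 7.7 points; remission rises only 3.8 or 2.8.
- Constant point drop: remission rises 41.5 − 27.6 = 13.9 or 43.3 − 33.1 = 10.2 points; response moves by 0.5 or less.

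With baseline SD 5, the same shift lowers response by 10.3 or 7.7 points (proportional) or raises remission by 11.9 or 9.0 points (constant).

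**ISI change.** Under a constant point drop, the mean change does not depend on the starting score. Under a proportional drop it does: 0.473 × 18 = 8.5 points against 9.8.

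**Does adjustment remove it?** Standardised rate = Σ w(b) × rate(b), where w(b) is the pooled share of Veterans with initial ISI b. For 20.7 against 18:
- Proportional drop, SD 0.2: response goes from 66.9% vs 56.4% to 61.6% vs 61.7%.
- Constant drop, SD 4.3: remission goes from 27.6% vs 41.5% to 34.5% vs 34.6%.

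The gap closed to within 0.1 point in every scenario. Restricting to initial ISI of 15 or more did not close it: the same two comparisons still give 70.1% vs 64.8% and 24.3% vs 34.6%.

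**The case against.** The strongest objection is that the documents contain no ISI by phase. The mailing example in Table 3 targets Veterans who already have an insomnia diagnosis or a sedative-hypnotic prescription, which does not point to a milder intake. That stands. A reader might infer that baseline severity is likely to shift, or shift downwards; the text supplies a mechanism and no more.

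The size also depends on the model. A reader might infer from the proportional-drop rows that response is bound to fall, or that response and remission will move in opposite directions. With a constant point drop, response is almost flat and only remission moves materially.

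The rates are supplementary. Reach is primary, Effectiveness is mainly ISI change, and no formal phase test of either rate is specified. The descriptive ISI scores might reveal a shift. This limits the consequence, but the planned phase comparisons remain and nothing corrects them. The mixed model does use the initial ISI, as a repeated outcome; that neither adjusts the two rates nor lets the drop depend on the starting score.

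A reader might also infer that the definitions are at fault, and that remission should become final ISI below 8 among Veterans starting at 8 or more. The numbers do not support that. As mean initial ISI goes from 20.7 to 16, that measure moves from 25% to 42%, against 23% to 32% for the plan's remission, under a proportional drop with residual SD 4.5 points. Under a constant drop it moves from 29% to 57%, against 28% to 50%. The response clause dampens the drift. Veterans starting at 7 or less can meet neither definition, but they are only 0.1% to 2.4% of the simulated intake, and the Table 2 assessment already screens for insomnia.

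**Conclusion.** The point holds as a missing adjustment. Effectiveness is to be compared between phases, the bundle can alter who starts treatment, and initial ISI appears in no named adjustment. If mean initial ISI differed by 2.7 points (20.7 against 18) with equal treatment, one crude rate would move by roughly 8 to 14 points: response if the drop is proportional, remission if it is constant. A more severe intake would reverse the signs. These sizes rest on the assumed baseline SD, spread of drop and severity shift, none of which the documents give. A related gap comes first: the Effectiveness model has no phase term, so the comparison that needs adjusting is not yet written. The outcome is secondary, and this is a free improvement to the analysis text.

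**What to change.** In section 5.6:

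1. Report the distribution of initial ISI by phase.
2. Make any between-phase comparison of response and remission with initial ISI in the model, or with rates standardised to one common initial ISI distribution.
3. For ISI change, specify a phase comparison that lets the drop depend on initial ISI: either final ISI on phase adjusted for initial ISI, or the repeated-measures model with time-by-phase and baseline-by-time terms. Adding initial ISI to that model as a main effect only would not do this: it shifts all of a Veteran's scores together and leaves the change over time unadjusted.

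Keep the section 5.5 definitions of response and remission, with no ISI limit on the denominator. The initial ISI is already extracted, so the cost is a few lines of text and some extra model terms, with no new data.

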## 5.1 Study Procedures

### 5.1 Study Design

Overview of Experimental Design and Timeline. This is a four-year, stepped-wedge, hybrid III implementation-effectiveness trial comparing two conditions: training PCMH clinicians to deliver BBTI (BBTI) vs. training clinicians to deliver BBTI augmented by access to, and support for, a bundle of expert-consensus implementation strategies (BBTI+IS). The goal of this trial is to determine if a bundle of implementation strategies can improve the uptake and sustainable delivery, and treatment outcomes, of BBTI in VA PCMH settings. Three approaches will be used to measure outcomes: (1) RE-AIM framework; (2) CFIR-guided qualitative interviews, with site PIs and PCMH clinicians, to identify barriers and facilitators related to implementation outcomes; and (3) surveys, completed by site PIs and PCMH clinicians, to identify utilization of specific implementation strategies. Four sites were invited to participate (Baltimore, Durham, Minneapolis, and Philadelphia) with Pittsburgh serving as the coordinating site, responsible for: (1) oversight of all study activities, (2) development and conduct of BBTI training, (3) providing support for the implementation strategies, and (4) directing data collection and analysis efforts.

As depicted in Figure 2, after study start-up procedures, the first step will involve training PCMH clinicians in BBTI at all sites. After BBTI training, site 1 (randomly selected) will have immediate access to, and support for, the bundle of implementation strategies for 12-months; this is the implementation phase of the trial. Sites 2, 3, and 4 will enter the pre-implementation monitoring phase for 6-, 12-, and 18-months, respectively, followed by their own 12-month implementation phase (random order). After each site has completed their 12-month implementation phase, access to the implementation strategies will be removed and each site will begin a 6-month post-implementation monitoring phase; however, for sites 1-3 we will continue to collect data to evaluate long-term sustainability through study month 39. Data collection will occur through all phases of the trial.

Figure 1. Study timeline.

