Session 3 (<30 minutes). The Veteran and clinician will review sleep diaries and adjust the sleep/wake schedule as needed. If time to fall asleep and time awake at night are <30 minutes most nights since session 1, the Veteran can extend their sleep schedule by 15 minutes, advancing the bedtime or delaying the wake time. If time to fall asleep and time awake at night are >30 minutes most nights, the sleep schedule is restricted/reduced by 15 minutes. Adherence to treatment recommendations is reinforced.

Session 4 (<20 minutes). The final session addresses treatment difficulties, reviews progress made and treatment gains, and relapse-prevention techniques are discussed. The four rules are emphasized, as is the process of measuring and titrating sleep in the future.

**Clinician BBTI Training.** Each site, in month 3 (see Figure 2), will have a group training led by the site-PI (face-to-face) and joined by [name] and/or Drs. [name] and [name] by video or phone. Topics covered will include: (1) normal vs. abnormal sleep, sleep stages, (2) the two-process model (homeostatic + circadian processes), (3) the etiology of insomnia (e.g., 3P model), and (4) assessment and diagnosis. Training will cover use of the PCMHI 5A functional assessment (see Table 2). Training will also cover triaging complex cases as not all Veterans who present to Primary Care with an insomnia complaint are appropriate for PCMHI. A referral to a higher level of care (e.g., specialty mental health, sleep medicine) is an option as part of the shared decision-making process. Triage a Veteran with complex insomnia is similar to triaging a Veteran with complex psychiatric symptoms, which is a standard procedure for PCMHI clinicians.

The VA CBT-I intake, per the EBP training, can serve as a model for a PCMHI insomnia intake, which will be modified to fit the PCMHI 5A evaluation: assess, advise, agree, assist, and arrange (see Table 2). Adaptation of BBTI will also be covered, including multi-modal delivery of care (e.g., in-person, phone, video) and how to integrate additional therapeutic techniques that may enhance treatment adherence and outcomes (e.g., behavioral activation, motivational interviewing). Treatment documentation and the utility of the BBTI templated note will be discussed as will the value and importance of involving Veterans in care and learning from them on how to improve delivery of insomnia treatment in the Primary Care setting.

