Adoption will be measured in two ways: (1) the number of PCMH clinicians who undergo training in BBTI relative to the number of PCMH clinicians eligible for training; and (2) the number of PCMH clinicians who treat at least one Veteran with BBTI relative to the total number of PCMH clinicians trained.

Implementation, or treatment fidelity, will be measured by rating mock treatment sessions with enrolled PCMH clinicians; ratings will be completed by site PIs using the BBTI-CRS. All enrolled PCMH clinicians will be rated following BBTI training, and then quarterly thereafter. They will receive clinical feedback by their site PI, as needed, and, if they score below the competency cutoff (<50% or <2 per item; 2=satisfactory), any necessary re-training from their site PI. If PCMH clinicians pass three consecutive mock sessions, they have the option of

discontinuing the mock sessions until mock session ratings at the end of the implementation phase and the end of the post-implementation phase. The BBTI-CRS scores will be used to develop an “implementation score” for each site—the average ratings across each site’s enrolled PCMHI clinicians.

As a secondary measure of Implementation, all enrolled PCMHI clinicians will have a random selection of BBTI progress notes reviewed, by their site PI, to assess BBTI elements being utilized (10% or at least 1 per month of eligible notes). Clinicians who neglect important BBTI elements (e.g., discuss 4 rules, assess with ISI, titrate TIB) will receive clinical feedback from their site PI. Each site’s secondary “implementation score” will be the average number of important elements across enrolled PCMHI clinicians reviewed progress notes. Though previous trials of BBTI have used audio-recorded sessions to measure Implementation, feedback from clinicians (current and prior studies) has suggested that audio-recording sessions were considered intrusive to delivering clinical care and limited rapport building with Veterans.

While not recording sessions is a less precise measure of Implementation/treatment fidelity, recorded sessions from the PI’s CDA found that clinicians consistently delivered treatment with competency (cutoff >50%; session 1 M=78% [SD=13%]; session 3 M=94% [SD=5%]) and only one rated session for a single clinician was below the 50% cutoff (47.5%).

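### Clinicians may stop BBTI-CRS ratings after three passes and no end-of-control rating is required, so late control-phase fidelity at sites 3 and 4 may be missing or selectively observed

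*Combined protocol and SAP*

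**What the plan says.** Section 5.5 (Study Evaluations) defines the measure: "Implementation, or treatment fidelity, will be measured by rating mock treatment sessions with enrolled PCMH clinicians", scored by site PIs on the BBTI-CRS. On timing: "All enrolled PCMH clinicians will be rated following BBTI training, and then quarterly thereafter". A clinician with three passes in a row may then choose to stop, on these terms: "discontinuing the mock sessions until mock session ratings at the end of the implementation phase and the end of the post-implementation phase". The end of the pre-implementation phase is not on that list. The site-level score is described as "the average ratings across each site", taken over its enrolled clinicians. As a secondary fidelity measure, the site PI reviews a random sample of each enrolled clinician's BBTI notes, with no stopping option.

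Section 5.1 sets the calendar. On training: "Each site, in month 3 (see Figure 2), will have a group training led by the site-PI". Site 1 goes straight into implementation. For the others: "Sites 2, 3, and 4 will enter the pre-implementation monitoring phase for 6-, 12-, and 18-months, respectively", and then 12 months of implementation and 6 months of post-implementation.

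Section 5.6 analyses Implementation, with other RE-AIM outcomes, in generalized linear mixed models. These have a fixed effect for phase and random effects for clinician and site. Pre-implementation versus implementation is the primary comparison. No term for calendar time or time since training is listed, and nothing is said about ratings missing because a clinician used the option.

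**The concern.** Aim 1 hypothesises better treatment fidelity under BBTI+IS. That needs a sound control-phase value, and all control time beyond month 6 after training lies at sites 3 and 4. While sites 1 and 2 receive the bundle, sites 3 and 4 are the concurrent controls.

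The option ties the required ratings to the ends of implementation and post-implementation, but not to the end of the comparator. Clinicians who use it at sites 3 and 4 contribute only early post-training ratings to the control phase. Their next required rating comes after a full year of bundle support. Whether a late control rating is required depends on earlier scores, so the ratings that remain may be a selected set. Once a site crosses over, the missing rating cannot be recovered.

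**Working it through.** **Calendar.** Phase lengths are from section 5.1. For site 4, training in month 3 + 18 control + 12 implementation + 6 post-implementation = 39, which matches the stated end of data collection. Below, months count from training, with ratings due at 0, 3, 6 and so on.

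**Earliest stop.** The text does not say whether the post-training rating counts as one of the three passes.
- Reading (a), it counts: passes at 0, 3 and 6, so the last rating before stopping is at month 6.
- Reading (b), it does not: passes at 3, 6 and 9, so the last is at month 9.

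**Unrated control time** = control length minus month of last rating (not below 0). **Gap** = end of implementation minus month of last rating.

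| Site | Control ends | Implementation ends | Unrated control months, (a) / (b) | Gap to next required rating, (a) / (b) |
|---|---|---|---|---|
| 1 | 0 | 12 | 0 / 0 | 6 / 3 |
| 2 | 6 | 18 | 0 / 0 | 12 / 9 |
| 3 | 12 | 24 | 6 / 3 | 18 / 15 |
| 4 | 18 | 30 | 12 / 9 | 24 / 21 |

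Full quarterly rating would give 5 control occasions at site 3 (0 to 12) and 7 at site 4 (0 to 18). The option removes up to 2 of 5 and 4 of 7 under (a), or 1 of 5 and 3 of 7 under (b). At site 2 the month 6 rating falls on the phase boundary, so nothing is lost there.

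**How many could stop at the earliest date.** Section 5.5 reports prior session 1 scores of 78% (SD 13%) against a 50% cutoff. Assuming normal scores, independent sessions and the total-score rule:
- z = (50 - 78)/13 = -2.15, so P(pass) = 98.4%
- P(three in a row) = 0.984³ = 95%
- With the session 3 scores (94%, SD 5%), z = -8.8 and essentially everyone passes.

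Those were recorded sessions, and sections 5.1 and 5.5 also mention a per-item cutoff, so pass rates could be lower. For assumed per-session pass rates:
- 0.7³ = 34%
- 0.8³ = 51%
- 0.9³ = 73%

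High pass rates leave few late control ratings. Lower ones leave more, but selected on performance.

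**Effect on the comparison.** At site 4 under (a), a clinician who stops has control ratings at months 0, 3 and 6 and then none until month 30. With phase as the only fixed effect, any change over those 24 months is attributed to phase.

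**The case against.** Several points on the other side are sound.

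- **Fidelity is still observed.** Note review continues for all enrolled clinicians (10%, or at least 1 per month, of eligible notes). A reader might infer that late control fidelity is unmeasured; it is not. But the review counts documented elements, needs BBTI notes to exist, and is the declared secondary measure. It does not replace a competency rating.
- **Stopping is optional.** A reader might infer that late control ratings come only from the weakest clinicians. The text does not support that: passers may continue, and late enrollees or clinicians with one failed session also remain. The supportable statement is that required ratings fall on those without three consecutive passes.
- **A clinician-level model is already planned.** Eligibility to stop depends on observed scores, so clinician random effects can largely absorb a changing mix of raters' subjects, though the choice to stop may have other causes. They cannot supply the missing rating or separate phase from time.
- **Bias toward the bundle is not shown.** A reader might infer that the site score would rise spuriously when passers return. Take four invented, unchanging site 4 scores of 80, 75, 70 and 48 under (a). Averaging by occasion, control is (3 × 68.25 + 4 × 48)/7 = 56.7 and implementation is (3 × 48 + 68.25)/4 = 53.1, a fall of 3.6. Pooling all ratings gives 1,011/16 = 63.2 and 417/7 = 59.6, again a fall of 3.6. Averaging within clinician first gives 68.25 in both phases, so no change. A spurious gain appears only if the control-phase average is set against the single end-of-implementation occasion (68.3 against 56.7), which is not the phase comparison in section 5.6. The example also needs a clinician who keeps failing despite the planned re-training, while the prior study had one rated session below the cutoff.
- **Reach, not fidelity, is the primary outcome**, which limits the importance of the point.

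**Conclusion.** The point holds as a gap in the main fidelity measure. BBTI-CRS ratings may be missing or selectively observed for the last 3-6 months of control at site 3 and the last 9-12 months at site 4, with no analysis plan for the gap. About 95% of clinicians could stop at the earliest date if mock sessions resemble the prior study's session 1, on the normality and independence assumptions above; the figure is 34-73% at assumed pass rates of 0.7-0.9. How many would use the option is unknown.

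Because the model has no time term, practice or drift would be read as a phase effect. Neither the direction nor the size of that bias can be established from the documents. This is an inexpensive improvement to a non-primary outcome and does not threaten the Reach analysis.

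**What to change.** In section 5.5, add the end of the pre-implementation phase to the two end-of-phase ratings already required. It should apply to all enrolled clinicians, including those who have used the stopping option. State whether the post-training rating counts toward the three passes. In section 5.6, analyse clinician-level end-of-phase ratings in the planned mixed model and keep the site average as a descriptive summary.

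This restores late control data and gives two same-time contrasts: site 3 at the end of control with site 1 at the end of implementation (both month 12), and site 4 with site 2 (both month 18, since 6 + 12 = 18). It reduces confounding with time since training but does not remove it, because a clinician's end-of-control and end-of-implementation ratings remain 12 months apart.

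The cost is one extra mock session per opted-out clinician at sites 3 and 4, with the same raters and form. At the recruitment floor in section 5.2 that is 2 × 2 = 4. If every clinician in Table 1 enrolled and opted out, the maximum would be between 9 + 14 = 23 and 19 + 18 = 37, depending on which sites are randomised third and fourth.
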